## **Hypothesis**

There is limited guidance on the optimal management of buprenorphine perioperatively and both buprenorphine discontinuation and continuation are acceptable standards of care. Buprenorphine continuation at low analgesic dosing is also accepted, however is not provided as a potential treatment strategy by SAMHSA. There is the risk of inadequate pain control necessitating opioid

escalation when buprenorphine is continued. Preliminary clinical observations support buprenorphine continuation at low analgesic doses (8mg) as it adequately facilitates postoperative pain management without interrupting OUD treatment, however to date, no prospective trial has investigated this treatment strategy in comparison to low dose buprenorphine continuation. Since optimal perioperative dosing strategies remain unknown, the purpose of this study is to investigate if buprenorphine continuation at analgesic dosing is superior to buprenorphine continuation in individuals presenting for elective surgery.

### Specific Aims

**Aim 1:** To compare the efficacy of perioperative standard of care low dose buprenorphine continuation (STD-BUP) to full dose continuation (FULL-BUP) in adults maintained on buprenorphine for OUD. *Hypothesis 1: Postoperative pain scores at postoperative day (POD) 1 will be higher in FULL-BUP patients compared to STD-BUP patients and this difference will be clinically significant (defined as a > 20% difference in pain scores between groups).* We will measure pain using a numeric rating scale (NRS) of 0 to 10, a standard tool used in comparing analgesic efficacy between distinct treatment interventions.

**Aim 2:** To compare postoperative opioid consumption (excluding buprenorphine formulations) in adults maintained on buprenorphine for OUD, measured as morphine milligram equivalents (MME) at 24, 48 and 72 hours postoperatively. *Hypothesis 2: FULL-BUP patients will have higher opioid consumption at 24, 48 and 72-hours postoperatively compared to STD-BUP patients.*

**Aim 3:** To compare OUD symptom severity and depressive symptoms; measured preoperatively and 30 days postoperatively using the Patient Health Questionnaire-9 (PHQ-9), Current Opioid Misuse Measure (COMM), and Opioid Craving Scale (OCS) instruments. *Hypothesis 3: There will be no difference in OUD symptom severity and depressive scores FULL-BUP patients compared to STD-BUP patients, both on day of surgery and at 30 days postoperatively.*

**Aim 4:** To compare the number of opioid prescriptions and quantity (in MME) of opioid medications dispensed, up to 30 days following surgery. *Hypothesis 4: The number of opioid prescriptions and the quantity of MMEs dispensed will be higher*

*for FULL-BUP patients than for STD-BUP patients during the 30 day period following surgery.*

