Our proposed study will provide data to improve acute pain management delivery for the growing population of individuals receiving buprenorphine as OUD therapy. Not only will our study address a considerable gap in care delivery, but it will help establish consensus for a topic that currently has mixed opinion. If this clinical trial identifies that buprenorphine dose reduction is no different than full dose buprenorphine continuation, than we can change our MaineHealth guidelines to recommend continuation without having to make any adjustments to patient's OUD treatment. If, however, we identify that patients with full buprenorphine continuation use more opioids and have prolonged hospital courses, it will confirm the need for our current guidelines, confirming our preliminary findings of adequate pain control with buprenorphine continuation at analgesic dosing. Additionally, it could help establish treatment plans where patients are provided with less opioids both as inpatients and outpatients decreasing opportunities for diversion and opioid related relapse. We will further explore the comprehensive effect of buprenorphine management strategies through engaging representatives from the substance use disorder community and the providers involved in the various phases of their care. Convening this group of stakeholders together as members of our Data Safety and Monitoring Review Board will help us identify the key concerns for patients with OUD. It will also allow us to tailor our study to address these issues, with the ultimate goal of reducing perioperative OUD severity and the risks associated with relapse.

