elective surgery who are taking  $\geq 12$ mg buprenorphine for OUD treatment will be eligible for this study. Enrolled participants will be randomized to receive either a reduced analgesic dose of buprenorphine (8mg) or to continue buprenorphine on the day of surgery without dose reduction. Our primary outcome of interest is postoperative pain scores. Our secondary outcomes of interest are opioid consumption, opioid dispensing up to 30 days following the surgical procedure and OUD related symptoms, including opioid withdrawal, cravings and relapse. We hypothesize there will be a clinically significant increase in pain scores when buprenorphine is continued in full compared to when it is continued at a lower analgesic dose. We will define clinical significance as a difference in composite pain scores of greater than 20% between groups. We also hypothesize that opioid consumption and opioid dispensing will be greater with full dose buprenorphine continuation compared to low-dose continuation. This will be the first randomized trial comparing competing perioperative buprenorphine treatment strategies and will yield critical preliminary data for larger, confirmatory studies. Additionally, we envision that this study will lay groundwork for follow-up investigations in this patient population, focused on preventing opioid cravings and relapse perioperatively, along with other clinical scenarios where acute pain is anticipated, such as intensive care unit settings.

Successful execution of this prospective trial will provide [name] with the tools and critical experience necessary to pursue her aspirations of becoming a successful clinical investigator. [name] has a mentorship team that is committed to her success and is led by her department chair, [name]. Her mentorship team also includes [name], [name], [name], [name], [name] and [name]. Her mentorship team will help provide guidance as she mentors residents, including [name], that have expressed interest in engaging in clinical research. They will meet with her periodically and provide her with any feedback that is required, based upon the trial phase, to help promote successful trial completion.

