### ***Biostatistical Analysis***

#### **Sample Size:**

We estimated study size based on postoperative pain scores in a recent study of surgical patients at our institution (manuscript submitted); mean NRS was  $50 \pm 28$ . Our estimate for effect size is based on published data showing that a difference in NRS of 20/100 points is clinically significant. A sample size of 32 per group will have 80% power to detect a difference in means of 20 (the difference between a Group 1 mean,  $m_1$ , of 50 and a Group 2 mean,  $m_2$ , of 30) assuming the common standard deviation is 28 using a two group t-test with a 0.05 significance level. To account for dropout, we will enroll an additional 8 patients for each group for a total sample size of 80 patients.

Statistical Analysis:

Data will be summarized using descriptive statistics and will be presented as means (SD), medians [IQR] or frequency counts (%), as appropriate. Data will be analyzed on an intention to treat basis. We will first examine the success of randomization by comparing covariates demographic and clinical covariate measurements between the FULL-BUP and STD-BUP groups; to conserve study power, no formal statistical comparison will be performed and the data will be reviewed visually. Next we will perform univariate analyses to compare outcome measures between the FULL-BUP and STD-BUP groups, using a two-sided t-test or Mann Whitney U test for continuous variables and chi square or Fisher exact tests for categorical data, as appropriate. For paired analysis of pre/post surgery instruments, we will use McNemar's test or the Wilcoxon test, as appropriate. We will then explore the relationships between demographic and clinical variables and outcome measures in bivariate analyses, using the above methods or Pearson's and/or Spearman's correlation, ANOVA or Kruskal-Wallis test, as appropriate. Finally, we will explore further any observed differences in outcome measures between study arms by adjusting for covariates using analysis of covariance or (in the event of missing data), mixed models regression. Covariates will be entered into the model if they demonstrate a significant ( $p \leq 0.1$ ) association with outcome measures in bivariate analyses.

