We will perform an interim analysis at 50% enrollment and will terminate the study if a significant pain score difference is detected. Significance for the interim analysis will be accepted at  $p < 0.003$ , based on 2 sequential tests and using an O'Brien-Fleming spending function to determine test boundaries. Significance overall will be accepted at  $p < 0.047$  to account for interim analysis. All statistical analyses will be performed by the Navigation team at CORE using SPSS Statistical Software version 27 (IBM SPSS Inc., Armonk, NY).

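### Does asking for a pain difference above 20% cut the chance of confirming Hypothesis 1 from 80% to about 50%?

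*Combined protocol and SAP*

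**What the plan says.** Specific Aims, Aim 1, predicts higher pain scores on postoperative day 1 with FULL-BUP and continues that "this difference will be clinically significant (defined as a > 20% difference in pain scores between groups". The Significance section repeats the idea for the composite score: "We will define clinical significance as a difference in composite pain scores of greater than 20% between groups". Neither place says whether the percentage is of the scale or of a group mean, or whether it applies to the observed difference or to a confidence limit.

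Under Biostatistical Analysis, the Sample Size paragraph works in points. It relies on "published data showing that a difference in NRS of 20/100 points is clinically significant" and states: "A sample size of 32 per group will have 80% power to detect a difference in means of 20". The planned means are 50 and 30, with a common SD of 28 and a 0.05 level. Eight more patients per group are added for dropout, which gives 40 per group.

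The Statistical Analysis paragraph compares outcomes "using a two-sided t-test or Mann Whitney U test for continuous variables", after group summaries as means (SD) or medians [IQR]. The interim paragraph says the sponsor "will terminate the study if a significant pain score difference is detected", at p < 0.003, and sets the overall level at p < 0.047. None of these steps refers to 20% or to 20 points. A short stretch of text between the interim paragraph and Limitations was not available for this check.

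**The concern.** Three places link clinical significance to the number 20, so it is natural to read them as one threshold. On that reading Hypothesis 1 has two parts: pain is higher with FULL-BUP, and the excess is more than 20 points. The power statement covers only the first part. With a true difference of exactly 20, the second part fails half the time at any sample size.

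A result could then be statistically significant yet at or below the plan's own clinical threshold, and the plan does not say how it would be described. The Background section raises the stakes: "If this clinical trial identifies that buprenorphine dose reduction is no different than full dose buprenorphine continuation, than we can change our MaineHealth guidelines". If it is unclear whether such a result counts as different, the choice could be made after the data are seen, in a trial where patients and treating staff know the assignment.

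**Working it through.** **Inputs.** True difference 20 (means 50 and 30), SD 28, 32 per group evaluable or 40 per group enrolled, and two-sided 0.05 for sizing (Sample Size and Statistical Analysis paragraphs). Final level 0.047 and interim level 0.003 (interim paragraph). Allocation 1:1 (Randomization Plan).

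**1. The plan's own figure.** The standard error of the difference is SD × √(2/n).
- n = 32: 28 × √(2/32) = 7.00. Exact noncentral-t power at a true difference of 20 is 80.3% at 0.05 and 79.5% at 0.047. With 31 per group it is 79.0% at 0.05, so 32 is the right size.
- n = 40: 28 × √(2/40) = 6.26. Power is 88.4% at 0.05 and 87.8% at 0.047.

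The stated 80% is correct for rejecting zero difference.

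**2. Smallest significant difference** (critical t × SE, level 0.047): 14.2 points with 32 per group and 12.6 with 40.

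**3. Threshold read as 20 scale points, judged on the observed difference.** P(observed > 20 | true 20) = 1 − Φ((20 − 20)/SE) = 1 − Φ(0) = 50%, whatever the SD or n. Both cut-offs in step 2 lie below 20, so adding the significance requirement leaves the figure at 50%. A simulation of 400,000 trials gives 49.9% (n = 32) and 50.1% (n = 40).

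Significant results at or below 20 points make up the rest: about 79.5 − 50 ≈ 30% of trials with 32 per group and 87.8 − 50 ≈ 38% with 40. With the interim look included, the shares are 28.0% (16 then 32 per group) and 35.8% (20 then 40). An 80% chance of observing more than 20 would need a true difference of 20 + 0.8416 × 7.00 = 25.9 (n = 32) or 20 + 0.8416 × 6.26 = 25.3 (n = 40).

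**4. Threshold read as a relative 20%.** At the planned means this is 0.20 × 50 = 10 points or 0.20 × 30 = 6 points. Both lie below the cut-offs in step 2, so in practice every significant result in the expected direction also passes the threshold. The simulated joint chance equals ordinary power: 79.5% (n = 32) and 87.8% (n = 40) at 0.047.

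**5. Threshold applied to the lower confidence limit, in points.** The chance at a true difference of 20 is about 2.3%.

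**6. Interim stop.** At SD 28, p < 0.003 needs an observed difference of about 28.1 points with 20 per group, or 32.0 with 16. An early stop would exceed 20 points in any case.

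| Reading of the 20% | Chance of meeting it with significance, true difference 20 (n = 32 / n = 40) |
|---|---|
| 20 points, observed difference | 50% / 50% |
| Relative, 6 to 10 points | 80% / 88% |
| 20 points, lower confidence limit | about 2.3% / 2.3% |

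**The case for a change.** The strongest argument for a change has three parts.

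First, the points reading has real support. The only source given for clinical significance is in points, and means of 50 and 30 differ by 40% of the larger or 67% of the smaller, so a relative 20% does not match the difference used for sizing. This makes the points reading plausible, but it does not settle it: where the plan means points it writes them as points.

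Second, the p-value and the threshold can disagree on either reading. On the relative reading, about 15 to 17% of trials with 32 per group, or 8 to 10% with 40, would pass the threshold without being significant. That is correct. But statistical and clinical significance can part company in any trial, and readers resolve this by looking at the size and precision of the estimate.

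Third, the Significance section words the threshold as a definition, and the Background section ties a guideline change to the result. The definition stands, but it is attached to a statement of what the investigators expect. The available decision rule is p < 0.047, and no passage makes the threshold a second condition. The branch in the Background section that would support keeping the current guideline turns on opioid use and length of hospital course and sets no pain-score threshold. The Significance section also presents the trial as a source of preliminary data for larger studies, which fits poorly with a two-part confirmatory criterion.

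It is fair to note that no confidence interval is planned and that a Mann-Whitney test gives no mean difference. Where means and SDs are reported, the difference and its interval follow from them and the group sizes. Where medians are reported instead, the difference in medians can still be set against 2 points on the 0–10 scale.

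**Conclusion.** The concern does not call for a change. The sample size and the 80% power are correct for the test that the plan describes, and that test remains valid however the 20% is read. The 50% figure is sound arithmetic, but it rests on three assumptions: that the percentage means scale points, that it is judged on the observed difference, and that it is a condition for success. The first two are left open, and nothing in the available text supports the third. Given all three, 50% is the figure for any superiority trial whose true effect equals the difference it was sized on. No sample size alters it, so it reveals no fault in this design.

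What remains is missing detail: the base of the percentage and how it is judged are not stated. A competent analyst would report the difference between groups with its precision and discuss it against 2 points on the 0–10 scale. A stricter label based on the lower confidence limit would be met in only about 2.3% of trials at the planning difference, so it is no clear improvement. The absence of a rule is judged on the text available and would need another look only if the missing stretch made the threshold a success criterion.

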### **Safety**

We will ensure that appropriate plans are in place to guarantee the safety of enrolled subjects. All patients will be made aware of the possible risks associated with treatment group to which they are randomly assigned, as well as the risks inherent in experiencing postoperative pain. For instance, both groups are at risk of experiencing OUD symptom exacerbation. The use of opioid agonists and perioperative pain itself may be risks for OUD symptom exacerbation and relapse. Reduction of buprenorphine to 8 mg before surgery as well as full dose buprenorphine continuation can potentially lead to OUD relapse since exposing patients to opioids with similar properties to the agents they abused in the past as management of their acute post-surgical pain can serve as a trigger for relapse. However, this risk is inherent in the current MMC standard of care.

Another potential risk is difficult post-operative pain control due to buprenorphine continuation since the pharmacokinetics of buprenorphine may interfere with the effectiveness of full opioid agonists used for pain control. However, this risk is not greater than the current risk to patients, since full dose buprenorphine continuation is a practice endorsed by SAMHSA. If patients experience poorly controlled pain, they will receive opioid and non-opioid rescue analgesic agents such as nerve blocks or epidurals when indicated, ketamine infusions, and alpha agonist medications, as determined necessary by the treatment providers caring for the

patient. All participants will be transitioned back to their regular dose of buprenorphine when postoperative surgical pain has subsided as determined by their buprenorphine provider following hospital discharge. This transition will be coordinated with their buprenorphine provider, which is our current standard practice when buprenorphine is discontinued, or the dose is reduced, perioperatively.

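### Hypothesis 3 predicts no difference in OUD severity and depression, but the plan can support it only through a non-significant difference test

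*Combined protocol and SAP*

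**What the plan says.** Specific Aims, Aim 3, names three instruments (PHQ-9, COMM, OCS). Hypothesis 3 reads "There will be no difference in OUD symptom severity and depressive scores FULL-BUP patients compared to STD-BUP patients", and the comparison applies "both on day of surgery and at 30 days postoperatively". Hypotheses 1, 2 and 4 each predict higher values under FULL-BUP; only Hypothesis 3 predicts sameness.

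The Biostatistical Analysis section gives one between-arm method for all continuous outcomes: "using a two-sided t-test or Mann Whitney U test for continuous variables". The McNemar and Wilcoxon tests listed there are for paired pre/post data. Analysis of covariance or mixed models come last, to look further into differences already observed. The level is set in the interim-analysis paragraph: "Significance overall will be accepted at $p < 0.047$ to account for interim analysis".

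The sample size rests on the pain score alone: "A sample size of 32 per group will have 80% power to detect a difference in means of 20", "assuming the common standard deviation is 28 using a two group t-test with a 0.05 significance level". Eight more per arm are enrolled for dropout, making 40 per arm. The available text gives no SD, margin or power for any Aim 3 score. A part of the document following the interim-analysis paragraph was not available, so this absence is established only for the text that was.

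**The concern.** A difference test suits a hypothesis that predicts a difference. When the hypothesis predicts none, the same test rewards weak data: fewer patients, noisier scores or more missing questionnaires all make a non-significant result more likely, and so make the hypothesis look better supported. Without a margin or interval rule, the plan has no way to separate arms that are similar from data too sparse to tell.

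The outcomes matter to the trial's rationale. The Safety section says "Reduction of buprenorphine to 8 mg before surgery as well as full dose buprenorphine continuation can potentially lead to OUD relapse". The Background criticises earlier studies for not addressing relapse and OUD-related symptoms after surgery. If a non-significant Aim 3 result were reported as no difference, readers could take it as evidence that the two strategies are alike on craving, misuse and depression when the data would not exclude a moderate worsening in either arm.

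**Working it through.** **Inputs from the protocol.** 32 evaluable and 40 enrolled per arm; 1:1 allocation; two-sided test; level 0.047 (0.05 in the sample size statement); pain difference 20 and SD 28.

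**Assumptions.** A true difference of 0.5 SD; roughly normal scores with equal SDs. For the joint calculation, correlations of 0.3 to 0.6 between the three scores.

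**1. The plan's own figure.** Standardised difference d = 20/28 = 0.714. Noncentrality = d × √(n/2) = 0.714 × √16 = 2.86 on 62 degrees of freedom. Power at 0.05 is 80.3%, so 32 per arm is reproduced. At 0.047 it is 79.5%.

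**2. One Aim 3 score, d = 0.5, level 0.047.**
- n = 32: noncentrality 0.5 × √16 = 2.00, critical t 2.027, power 49.3%, miss rate 50.7%.
- n = 40: noncentrality 0.5 × √20 = 2.24, critical t 2.018, power 58.8%, miss rate 41.2%.
- At level 0.05 the miss rates are 49.6% and 40.2%. A Mann-Whitney test with 32 per arm misses about 53%.

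**3. Other effect sizes, level 0.047.**

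| True difference | Missed, 32 per arm | Missed, 40 per arm |
|---|---|---|
| 0.3 SD | 79% | 75% |
| 0.5 SD | 51% | 41% |
| 0.8 SD | 12% | 6% |

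The difference detectable with 80% power is 0.72 SD with 32 per arm and 0.64 SD with 40.

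**4. All three scores differ by 0.5 SD in the same direction (simulated, one time point).** All three tests are non-significant in about 20% (correlation 0.3) to 29% (correlation 0.6) of trials with 32 per arm, and in 13% to 20% with 40.

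**5. Precision.** The 95% CI half-width in SD units is t × √(2/n): 1.999 × √(2/32) = 0.50 with 32 per arm, and 1.991 × √(2/40) = 0.45 with 40.

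**6. Could the trial show similarity within ±0.5 SD?** With two one-sided tests at 0.05 (the 90% CI wholly inside the margin) and arms truly equal, success is about 26% with 32 per arm and 43% with 40. About 69 per arm would be needed for 80%. The ±0.5 SD margin is illustrative; the documents give none.

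**The case against.** The case on the other side has several parts.

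- **The decision rule is inferred.** Nothing in the available text says that a non-significant Aim 3 test will be reported as no difference, and the 0.047 level appears in a paragraph about interim stopping on pain. Both points are fair. The level hardly matters (step 2). On the rule, the plan offers no other route to supporting Hypothesis 3, which is why it should say how a null result will be read.
- **The 0.5 SD is a choice made for this review.** True. The figures depend on it, and step 3 gives others. The mismatch between hypothesis and test does not depend on it.
- **A miss rate of about half is for one score.** Correct. One significant result among three would contradict the hypothesis, so if all three scores worsen the joint figure of 13-29% applies. The single-score figure applies if only one does.
- **Baseline adjustment would help.** With an assumed pre/post correlation of 0.5, the effective difference is 0.5/√(1 − 0.25) = 0.577 SD, and the miss rate falls to 39% (32 per arm) or 29% (40). But the plan reserves covariate adjustment for exploring differences already seen.
- **OUD safety does not rest on these scores alone.** This stands. Study Procedures collects buprenorphine treatment retention, withdrawal and substance-use instruments are planned, and relapse, overdose, withdrawal and cravings go to the DSMB as adverse events.
- **The aim is secondary.** The Significance section describes the results as preliminary data for larger studies. This lowers the importance.

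A reader might infer that a null Aim 3 result would carry no evidential weight, or that the institutional guideline would turn on it. The documents do not support either. Power at 0.8 SD is 88-94%, and the guideline statement in the Background is not tied to Aim 3.

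**Conclusion.** The point holds in a limited form. Hypothesis 3 is a no-difference statement, and the available plan can support it only by failing to find a difference. With 32 to 40 per arm, a null result argues against between-arm differences of roughly 0.7 SD or more on a score, but is weak evidence against 0.5 SD and says little about 0.3 SD. These sizes rest on assumed effects in SD units, approximate normality, no loss beyond the eight per arm allowed, and unadjusted analysis. It should be corrected because the correction is cheap and changes what Aim 3 can conclude. It does not touch the primary pain comparison.

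**What to change.** In Specific Aims, replace Hypothesis 3 with an estimation aim: the between-arm difference in PHQ-9, COMM and OCS will be estimated with 95% confidence intervals on the day of surgery and at 30 days. Both time points should stay, since the hypothesis names both.

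In the Statistical Analysis text, add that a non-significant Aim 3 test will not be reported as no difference, and that the conclusion will state the largest difference in either direction that the interval does not exclude. Give the expected unadjusted half-width of about 0.45 to 0.50 SD beside it, so that readers know beforehand what can be ruled out.

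If a no-difference claim is to be kept, allow it only where the interval lies inside a margin fixed for each scale, with its reason, before the data are seen. Step 6 shows that such a claim would often fail at ±0.5 SD even if the arms were equal.

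The cost is a few sentences and intervals computed from data already planned, with no extra patients or visits. The price is a weaker secondary claim: a bounded estimate in place of a statement of no difference.
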